4.7 End of Treatment End of Trial

The end of trial date is defined as the last date of last contact with the subject. This does not refer to overall trial duration. The end of trial date and timing for follow-up assessments will be individualized for each subject.

Randomized subjects will have their last scheduled treatment 25 months from their date of randomization. If a subject discontinues IMP before Month 25, the last date that the subject received IMP will be recorded as EoTx.

4.8 Measures to Minimize/Avoid Bias

Only subjects who reach Day -1 and are who have indicated that they would likely be able to tolerate the minimum dose of IMP "for the rest of their lives" at a level of 45/15 mg for tolvaptan and of 500/500 mg for metformin will be eligible to enter the un-blind, randomized treatment period.

Immediately prior to randomization, and at all subsequent visits or site-subject contacts, the subject will be reminded of the importance of their commitment to continue participation in the trial.

Randomization will be 1:1, tolvaptan:metformin. Randomization process will be carried out by a WEB-based, internet-accessible, system (e-trial platform). Investigators willing to include a patient should log-in into the e-trial platform and complete the registration form.

Each patient will be informed via a cover letter (that is the informed consent form) including clear instructions on participation, drug use, dosing and prescription.

5. POPULATION OF THE STUDY

5.1 Number of Subjects and Sites

This trial will enroll approximately 150 tolvaptan and metformin naïve subjects affected by Type I-truncating ADPKD, as they have grater probability of progression (10). Moreover data from Tempo trials (3/4 and 4/4) (19,75) and from its post-hoc analysis (76) revealed that patient with faster disease progression had greater beneficial effects from therapy.

Male and female adults will be enrolled, from 18-50 years of age with eGFR greater than $45 \text{ ml/min}/1,73 \text{ m}^2$

The study will be conducted in about 11 Italian Hospital Nephrology Departments. Patients will be selected from local databases and subjects will be enrolled till the estimated sample size is achieved. Only subjects tolerating a run-in period of tolvaptan or metformin will enter the on-treatment period, in order to limit subsequent withdrawal due to lack of tolerability.

5.2 Inclusion Criteria

- 1) Men and women aged between 18 and 50 years
- 2) eGFR (CKD-EPI) ≥ 45 ml/min/1,73 m2
- 3) Genetic Diagnosis of Type I ADPKD truncating mutation
- 4) Signed and dated informed consent

5.3 Exclusion Criteria

1) Women of childbearing potential (WOCBP) who do not agree to practice 2 different methods of birth control or remain abstinent during the trial and for 30 days after the last

dose of IMP. If employing birth control, 2 of the following precautions must be used: vasectomy of partner, tubal ligation, vaginal diaphragm, intrauterine device, birth control implant, condom, or sponge with spermicide. Non-childbearing potential in women is defined as female subjects who are surgically sterile (ie, have undergone bilateral oophorectomy or hysterectomy) or female subjects who have been postmenopausal for at least 12 consecutive months.

2) Women who are breast-feeding and/or who have a positive pregnancy test result prior to receiving investigational medical product (IMP).

3) Treatment with acarbose, guar gum, cimetidin, phenprocoumon, oral anticoagulants, thrombolytic drugs, diuretics, ranolazin, cephalexin.

4) Evidence of active systemic or localized major infection at the time of screening.

5) Hepatic impairment or liver function abnormalities other than that expected for ADPKD with typical cystic liver disease during the screening period as defined by:

- AST O ALT >8x UNL
- AST O ALT >5x UNL >2 WEEKS
- AST O ALT >3x UNL E BT >2x UNL OR INR >1,5
- AST O ALT >3x UNL E SIGNS AND SYMPTOMS OF LIVER DAMAGE (fatigue, anorexy, nausea, vomiting, right hypocondrium pain, fever, jaundice, skin rash, itching)

6) Acute or chronic disease causing tissue hypoxia (e.g.: myocardial failure, severe arythmias, myocardial infarction, respiratory failure, liver failure, alcohol acute intoxication, alcoholism, dehydration).

7) Previously diagnosed diabetes already in treatment with other hypoglycemic drugs.

8) Ongoing breast feeding.

9) Use of any other investigational drug or treatment up to 4 weeks before enrollment and during the treatment phase.

10) Known hypersensitivity to metformin and its derivatives.

11) Psychiatric disorders and any condition that might prevent full comprehension of the purposes and risks of the study.

12) Malignancies within three years before enrolment in the study.

13) HIV, HBV, HCV infection.

14) Urinary tract obstruction.

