10.5.1 Requirements for Repeated Liver Testing

10.5.1.1 Repeated Liver Testing in Subjects with Normal Values at Screening

The appearance of any suspicious symptom or sign should trigger prompt testing of hepatic function (i.e., within 72 hours). Local laboratory testing is acceptable, ideally with a concurrent central laboratory sample for confirmation.

Any transaminase or bilirubin values which exceed 2 x ULN should also prompt immediate retesting within 72 hours. While values remain in an abnormal range, testing frequency should be increased to at least weekly for the first month, gradually returning to monthly/three monthly as indicated by the results.

Subjects exhibiting such an increase during the tolvaptan titration/run-in phases will be disqualified from randomization on safety grounds and should not be randomized.

Should the cause of the abnormality be determined to be unrelated to tolvaptan exposure (e.g., having identified a plausible alternative explanation) such a subject may be rescreened only with medical monitor approval.

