10.5.1.2 Repeated Liver Testing in Subjects with Abnormal Values at Screening

Subjects found to have liver laboratory abnormalities at screening or who have a history of non-ADPKD-related liver disease will require further evaluation. These subjects will need to have the special liver eCRF completed and additional testing will be required during screening (to confirm the stability of the abnormality) and during the tolvaptan run-in phase at least 1 week prior to randomization (to confirm eligibility for randomization).

Management of such subjects should be closely coordinated with the trial's Medical Monitor. In these subjects, further changes in liver test levels of > 2 x upper limit of their highest screening value at any point post-screening should prompt re-testing within 72 hours. Should such increase occur in the tolvaptan titration/run-in phase, the subject will be disqualified from trial.

10.5.1.3 Liver Test Abnormalities and Interruption/Discontinuation of Investigational Medicinal Product

Liver transaminase or bilirubin levels reaching or exceeding 2 x ULN that have an uncertain or rapidly increasing trajectory should prompt at least temporary IMP interruption. IMP should not be resumed until monitoring indicates abnormalities have resolved, are stable or are not rapidly increasing, and then only with an increased frequency of monitoring.

Subjects would not typically be allowed to resume treatment with IMP if they have:

- transaminase levels rise above 8 x ULN;
- transaminase levels are > 5 x ULN for more than 2 weeks; or
- concurrent elevations of transaminase > 3 x ULN and BT > 2 x ULN.

Subjects with these levels of abnormality may be re-challenged with IMP if abnormalities were adjudicated as having a < 50% likelihood of being related to IMP (per DILI network [DILIN] probability criteria) by the investigator and medical monitor.

All elevations will be assessed by the medical monitoring team. The subject must also be willing to comply with these monitoring measures, be informed of the potential risks, and consent to IMP re-challenge.

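### Liver entry limits repeat the no-resume limits, and the uncapped re-test trigger for patients abnormal at screening conflicts with them

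*Combined protocol and SAP*

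**What the plan says.** Section 5.3, item 5 excludes AST or ALT above 8 times ULN; a sustained elevation, written as "AST O ALT >5x UNL >2 WEEKS"; values above 3 times ULN with raised bilirubin or INR; and values above 3 times ULN with liver signs and symptoms.

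Section 10.5.1.3 lists when drug would not typically be resumed. The list includes "transaminase levels rise above 8 x ULN" and "transaminase levels are > 5 x ULN for more than 2 weeks".

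For patients normal at screening, section 10.5.1.1 uses a fixed level: "Any transaminase or bilirubin values which exceed 2 x ULN should also prompt immediate retesting within 72 hours". It adds: "Subjects exhibiting such an increase during the tolvaptan titration/run-in phases will be disqualified from randomization on safety grounds".

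For patients abnormal at screening, section 10.5.1.2 uses a relative level. Re-testing within 72 hours follows "further changes in liver test levels of > 2 x upper limit of their highest screening value", and "Should such increase occur in the tolvaptan titration/run-in phase, the subject will be disqualified from trial". It also asks for extra testing at screening to show that the abnormality is stable, for coordination with the Medical Monitor, and for a further test "during the tolvaptan run-in phase at least 1 week prior to randomization".

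**The concern.** Limits chosen for deciding whether a patient already on drug may go back on it are being used to decide who may start. Allocation is 1:1, so about half of those admitted will start tolvaptan, for which section 3.2 names acute liver injury as the related adverse event.

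The relative trigger is most permissive for the patients with the highest starting enzymes. A site could have a run-in result that calls for nothing under section 10.5.1.2 yet lies above a level at which section 10.5.1.3 says drug would not typically be resumed. The protocol does not say which rule governs. The one extra on-drug check aimed at these patients is tied to a date that does not exist in this design.

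**Working it through.** No power or sample-size figure bears on this point. The check sets the limits side by side and does simple arithmetic on the trigger and the visit days.

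**1. Entry limits against no-resume limits** (multiples of ULN)

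| Entry, 5.3 item 5 | No resumption, 10.5.1.3 |
|---|---|
| AST/ALT >8 | AST/ALT >8 |
| AST/ALT >5 for >2 weeks | AST/ALT >5 for >2 weeks |
| AST/ALT >3 with bilirubin >2, or INR >1.5 | AST/ALT >3 with bilirubin >2 |
| AST/ALT >3 with symptoms | not listed |

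All three no-resume limits are carried over. The entry list adds only INR and symptoms.

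**2. Who gets in.** Take a patient with no symptoms, normal bilirubin and INR, and AST or ALT above 5 and up to 8 times ULN, known for 2 weeks or less. No line of item 5 excludes this patient. Section 10.1.3 counts transaminases above 5 times ULN as a serious adverse event.

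**3. Can the duration limit be shown?** Section 4.1 gives screening 1 to 2 weeks, so samples are at most 14 days apart, and the limit needs more than 14 days. It can be shown only if screening is extended (4 extra weeks in section 4, 8 in section 4.1) or earlier results are used.

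**4. The relative trigger.** Let s be the highest screening value in multiples of ULN. I read section 10.5.1.2 as a trigger T = 2s.

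| s | T = 2s | Multiple of the normal-screener trigger, T/2 |
|---|---|---|
| 2.5 | 5 | 2.5 |
| 3 | 6 | 3 |
| 4 | 8 | 4 |
| 4.5 | 9 | 4.5 |
| 6 | 12 | 6 |
| 8 | 16 | 8 |

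T passes 5 when s exceeds 2.5, and passes 8 when s exceeds 4. Across the band 5 < s ≤ 8, T runs from above 10 to 16.

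**5. The conflict in one patient.** Screening value 6, end of run-in value 9. Since 9 < 12, section 10.5.1.2 requires neither a re-test nor disqualification. Since 9 > 8, the value is above the first no-resume limit in section 10.5.1.3.

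**6. Dates.** Randomisation is Day -29 (section 4) or Day -30 (section 4.2 heading). Titration starts on Day -28, and run-in is Day -7 to Day -1. A test at least a week before Day -29 falls on Day -36 or earlier, before any drug, while run-in starts 29 - 7 = 22 days after randomisation. No day meets both conditions. Titration contacts are phone calls (section 4.3), and Figure 1 shows no laboratory tests at the end of titration. The first dated on-drug liver test is therefore the end of run-in visit on Day -1, 28 - 1 = 27 days after the first dose.

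**The case against.** A reader might infer that patients abnormal at screening have no absolute stopping limit and could drift to 16 times ULN unchecked. The documents do not support that. Section 10.5.1.3 is not restricted to normal screeners. It calls for at least temporary interruption from 2 times ULN when the trajectory is uncertain or rapidly rising, and its no-resume limits apply to everyone. A patient moving from 6 to 12 times ULN would very likely be interrupted before reaching the section 10.5.1.2 trigger. Values above 5 times ULN are also reportable as serious adverse events, so they would not pass unnoticed.

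Nor is the 5 to 8 band admitted without scrutiny. Section 10.5.1.2 requires stability testing and Medical Monitor involvement, and screening can be extended. These safeguards narrow the gap, but none sets a numeric ceiling, and the interruption rule depends on a judgement about trajectory.

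A relative trigger is itself reasonable for chronically raised enzymes: a fixed limit of 2 times ULN would disqualify someone stable at 2.5. That argues for keeping the relative rule under a cap.

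The timing fault is partly one of wording. Sections 4.4, 4.8 and 10.5.1.1 use randomisation loosely, as if it came at or after run-in. If it means entry on Day 0, a test at least a week earlier and still within run-in could fall only on Day -7, where no clinic visit is scheduled.

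Finally, section 2.2 says tolvaptan will be used within its marketing authorisation. The label's liver limits are not in the documents, so whether they would bar some of these patients cannot be judged here.

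**Conclusion.** The point holds as a conflict between two rules together with a loose entry limit. Entry is open to symptom-free patients with normal bilirubin and INR and a recent AST or ALT of 5 to 8 times ULN. For any screening value above 4 times ULN, the section 10.5.1.2 trigger lies above the 8 times no-resume limit, and at the highest admissible single value it is 16 times ULN. The run-in check cannot be carried out as written if randomisation means allocation on Day -29 or -30.

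This rests on reading the trigger as twice the highest screening value. The documents do not say how many patients would be affected; it is probably few. The case for change is that the protocol's own numbers disagree on a safety matter and the correction is cheap. It does not rest on any estimate of expected harm.

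**What to change.** 1. In section 5.3, item 5, exclude AST or ALT above 5 times ULN regardless of duration. Keep the other lines. Section 10.5.1.2 already asks for proof of stability at lower values, so no further exclusion is needed.
2. In section 10.5.1.2, set the trigger at the lower of twice the highest screening value and the absolute limits: re-test at 5 times ULN at the latest, so that the 2-week limit can be judged, and stop drug at 8 times ULN at the latest. For a screening value of 4.5, re-testing moves from 9 to 5 and stopping from 9 to 8.
3. Replace disqualification from the trial with stopping drug and staying in follow-up. These patients are already randomised, section 12.3 analyses everyone randomised, and the disqualification rule names only the tolvaptan phases, so removals would fall on one arm.
4. Replace the timing before randomisation with two checks that fit the design: a stability test before Day -29/-30 and an on-drug liver test in run-in before Day 0.

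The cost is amendment wording. A few patients become ineligible, need extra re-tests or stop drug earlier. Someone admitted just under 5 times ULN will be re-tested after almost any rise.

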5.4. Withdrawal of Consent

All subjects have the right to withdraw their consent from further participation in the trial at any time without prejudice. The investigator can also discontinue a subject's participation in the trial at any time if medically necessary. Unless the subject provides their written withdrawal of consent or there is other written documentation by the investigator confirming the subject's verbal intent to completely withdraw from the trial, subjects should be followed for all protocol-specified evaluations and assessments.

Complete withdrawal of consent requires a subject's refusal also of all of the methods of follow up.

Withdrawal of consent is a critical trial event and therefore should be approached with the same degree of importance and care as is used in initially obtaining informed consent. The reasons for a subject's intended withdrawal need to be completely understood, documented and managed to protect the rights of the subject and the integrity of the trial.

A subject may initially express his desire to interrupt or discontinue IMP administration, which is not equivalent to a complete withdrawal of consent for further participation.

A subject may, however, indicate that further trial participation is creating a burden on their work or social schedule. Therefore, the investigator should determine if the subject can continue participation in the trial if modifications to his/her treatment and/or schedule of assessments can be accommodated.

Only subjects who withdraw their permission for all of the above degrees of follow-up are considered to have completely withdrawn their consent to participate in the study.

In all cases of impending IMP discontinuation or consent withdrawal, investigators will be given instructions to meet and discuss with the subject their options of continuing in the trial, preferably on therapy. The investigator should ensure understanding and documentation of the reasons for the subject's desire to withdraw consent.

If a subject in randomized treatment period wishes to withdraw from the trial:

The investigator should first seek to understand the subject's motivation and wherever possible make accommodations to prevent treatment discontinuation or complete withdrawal of consent and maintain the fullest compliance with

- 1. Participation in a subset of protocol specified follow-up procedures (by a frequency schedule and method as agreed by subject and staff).
- Participation in all regularly scheduled, study-related follow-up visits and EoTx visits.
- Contact of the subject by trial personnel, even if only by telephone, to assess current medical condition and obtain necessary medical or laboratory reports relevant to the trial's objectives.

42

- 4. Contact of alternative person(s) who have been designated in source records as being available to discuss the subject's medical condition, even if only by telephone, mail or e-mail (e.g., family, spouse, partner, legal representative, friend, neighbor, physician).
- Access to medical information from alternative sources (e.g., hospital/clinic medical records, referring doctor's notes, public records, dialysis, transplantation or vital registries, social media sources).

6. TREATMENT

6.1 Treatment dose and schedule

Subjects will be instructed to take the following doses for titration:

- 1 tablet 45 mg upon waking and 1 tablet 15 mg approximately 8 to 9 hours later for 1 week;
- 1 tablet 45 mg + 1 tablet 15 mg upon waking and 2 tablets 15 mg approximately 8 to 9 hours later for 1 week;
- 2 tablets 45 mg upon waking and 2 tablets 15 mg approximately 8 to 9 hours later for 1 week.

During run-in period, subjects will take the maximum dose of tolvaptan achieved during titration (or at least 45/15 mg).

For the Metformin titration period and subsequent run-in period, subjects will receive 2 packages at the first visit of metformin 500 mg.

Subjects will be instructed to take the following doses for titration:

- 1 tablet 500 mg upon waking for 1 week;
- 1 tablet 500 mg upon waking and 1 tablet 500 mg approximately 8 to 9 hours later for 1 week;

1 tablet 500 mg upon waking, 1 tablet 500 mg approximately 8 to 9 hours later and 1 tablet
 500 mg approximately 8 to 9 hours later for 1 week.

During run-in period, subjects will take the maximum dose of metformin achieved during titration (or at least 500/500 mg).

If the subject cannot tolerate the lowest permitted doses, he/she will be deemed a titration failure or a run-in failure.

During the on-treatment period, the patient will take the maximum tolerated dose achieved during titration and run-in. The subject will stay on that dose for the entire trial, if not otherwise contraindicated by AEs or not tolerated.

Patients on metformin experiencing eGFR reduction below 45 ml/min, can not take more than 1000 mg a day of metformin (thus reducing from 1500 mg a day to 1000 mg a day).

Those patients on Jinarc will receive 1 package containing 4 blisters (irrespectively of the dosage).

Those patients on Zuglimet will receive 2 packages (all containing 3 blisters of 10 tablets) if on 500/500 mg a day, 3 packages if on 500/500/500 mg a day.

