2.2.4 Justification for the route of administration, dosage and dosage regimens

Dose choice has been done on the basis of Takiar et al. study (7). They examined *"in vivo"* only one dose known to activate AMPK (daily i.p. injections of metformin 300 mg·kg⁻¹·d⁻¹ dissolved in a 5% dextrose solution). When considered on a simple milligram per kilogram body weight basis, this dose appears considerably higher than the current maximum dose

prescribed for patients with diabetes or polycystic ovary syndrome. However, humanequivalent dose extrapolation is calculated more accurately based on body surface area than on weight. When this calculation is performed for a 60-kg adult, the dose used in our mouse studies extrapolates to a daily dose of ~1,500 mg (7), well within the range in which metformin is safely used in humans.

After oral administration, metformin absorption is saturable and incomplete. It is assumed that the pharmacokinetics of metformin absorption is non-linear. For this reason, a split doses regimen has been chosen for metformin administration (one cap every eight hours).

Patients randomized to tolvaptan, will start the treatment according to AIFA indications (45 mg followed, 8 hours later, by 15 mg), then they will up-titrate (every week, if tolerated) to 60 mg + 30 mg and then to 90 mg + 30 mg.

Patients on metformin, will start to take metformin once a day (500 mg), between meals. Every week they will up-titrate to 500 mg twice a day (if tolerated) and then to 500 mg thrice a day.

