4.1 Screening Period (up to Day -30)

No investigational treatments will be administered during the screening period.

Preliminary eligibility for the trial will be initially assessed using the subjects' historical laboratory or imaging data.

During this period, the subject's eligibility for the trial will be confirmed using historical genetic test data and imaging data of the kidneys to support a diagnosis of ADPKD and to verify the level of CKD primarily due to ADPKD and not to other renal (hypoplasia) or metabolic (diabetic or hypertensive nephropathy) disorders.

Eligibility will be confirmed by the mean of eGFR calculated from the subjects' 2 pretreatment, central-lab, serum creatinine assessments (collected at least 24 hours apart). The final screening visit on Day -29 will not be scheduled until laboratory results from the second screening visit (V2) are received and evaluated. The eGFR values will be estimated based on the Chronic Kidney Disease-Epidemiology (CKD-EPI) formula. Subjects will be told that they will receive tolvaptan or metformin during the subsequent periods of the trial.

On Day -30, patients will undergo TKV measurement by means of Ct- or MRI-scan (if not already performed within the 6 months before the enrollment). Then, patients will be randomized to receive either metformin or tolvaptan and they will be told to start IMP assumption since the day after randomization.

Those randomized in metfromin arm will receive Zuglimet® 500 mg (2 packages, each of them containing 3 blisters; every blister contains ten 500 mg coated tablets).

Those randomized to tolvaptan arm will receive Jinarc® 45/15 mg (2 packages, each of them containing 4 blisters; every blister contains seven 15 mg tablets of and seven 45 mg tablets).

The screening period will last 1-2 weeks, but may be extended up to an additional 8 weeks for subjects who require modification of medical care or further medical evaluation specifically for this trial. This may include, for example, stabilizing anti-hypertensive regimens for subjects discontinuing diuretics or "wash-out" of other investigational agents.

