6.2.2 Packaging and labeling

All IMP will be provided to the investigator(s) by the promoter of the Coordinating Center or designated agent.

Tolvaptan (Jinarc®) will be provided as 3 types of packages:

1) package containing 4 blisters of tolvaptan. Each blister contains 14 tablets: 7 15 mg tablets (triangular, in a green background), and 7 45 mg tablets (squared, in a gray background);

2) package containing 4 blisters of tolvaptan. Each blister contains 14 tablets: 7 30 mg tablets (rounded, in a purple background), and 7 60 mg tablets (rectangular, in a golden background);

3) package containing 4 blisters of tolvaptan. Each blister contains 14 tablets: 7 60 mg tablets (rectangular, in a golden background); and 7 90 mg tablets (pentagonal, in an orange background).

Metformin (Zuglimet®) will be provided as a package containing 3 blisters. Each blister contains 10 500 mg tablets.

Each package used will be labeled to clearly disclose the subject identification number (ID), compound ID, trial number, Promoter's name and address, instructions for use, route of administration.

Each package of the designated IMP will be dispensed at the beginning of each specific period.

For the tolvaptan titration period and subsequent run-in, subjects will receive 2 cartons at the first visit of tolvaptan 45/15 mg.

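### No single listed tolvaptan package supplies the 90/30 mg top step for 28 days, and the first-visit tolvaptan supply does not cover a patient held at 60/30 mg through run-in

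*Combined protocol and SAP*

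**What the plan says.** **Dose steps.** After the 45/15 mg start, Section 2.2.4 says of tolvaptan patients: "then they will up-titrate (every week, if tolerated) to 60 mg + 30 mg and then to 90 mg + 30 mg". Section 4.3 gives the same steps, with 90/30 mg as the maximum. Section 6.1 writes the second titration step as "1 tablet 45 mg + 1 tablet 15 mg upon waking and 2 tablets 15 mg approximately 8 to 9 hours later" and the third as "2 tablets 45 mg upon waking and 2 tablets 15 mg approximately 8 to 9 hours later for 1 week". Patients then stay on their maximum tolerated dose throughout the trial, unless adverse events or intolerance prevent it.

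**On-treatment supply.** Section 6.1: "Those patients on Jinarc will receive 1 package containing 4 blisters (irrespectively of the dosage". The sentence gives no period.

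**Packages.** Section 6.2.2 lists three, each of four blisters. The first holds 15 and 45 mg tablets and the second 30 and 60 mg tablets. Of the third it says: "Each blister contains 14 tablets: 7 60 mg tablets (rectangular, in a golden background); and 7 90 mg tablets (pentagonal, in an orange background".

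**Titration and run-in supply.** Section 6.2.2: "For the tolvaptan titration period and subsequent run-in, subjects will receive 2 cartons at the first visit of tolvaptan 45/15 mg". Section 4.1 gives the content: "2 packages, each of them containing 4 blisters; every blister contains seven 15 mg tablets of and seven 45 mg tablets". For run-in, Section 6.1 says "During run-in period, subjects will take the maximum dose of tolvaptan achieved during titration (or at least 45/15 mg". Metformin patients receive two packages of 30 tablets for the same two periods (Sections 4.1 and 6.1). Titration contacts are phone calls (Section 4.3; Section 9.1.3, Titration period). The next dispensing is at the end-of-run-in visit on Day -1 (Section 4; Section 9.1.3, Run-in Period).

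**The concern.** A supply rule that ignores dose works only if each dose step has a package that makes it, one tablet of each strength a day. The first two packages fit the first two steps in this way. The third does not fit the third step, because it contains no tablet from which the 30 mg afternoon dose can be made. A site following Sections 6.1 and 6.2.2 literally could not keep a 90/30 mg patient on the assigned dose from one package.

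The titration supply raises a similar question. It is handed over once, up-titration depends on tolerability, and several dose paths are therefore permitted. A path that uses more 15 mg tablets than were supplied would run out during run-in, the week meant to confirm tolerability on a stable dose (Section 4.4).

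**Working it through.** **1. Days covered by one package**

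Inputs (Section 6.2.2): 4 blisters x 7 tablets = 28 tablets of each strength. The 28-day period is inferred from this count and from the 28-day month in Section 7; Section 6.1 does not state it.

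| Package | 45/15 mg | 60/30 mg | 90/30 mg |
|---|---|---|---|
| 15+45 mg | 28 | 9 | 14 |
| 30+60 mg | 0 | 28 | 14 |
| 60+90 mg | 0 | 0 | 0 |

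The one-package rule is reproduced at 45/15 mg and 60/30 mg with the matching package. At 90/30 mg:
- 15+45 mg: the afternoon dose takes two 15 mg tablets, so 28/2 = 14 days, with two 45 mg tablets each morning.
- 30+60 mg: the morning dose needs at least one 30 mg tablet and the afternoon dose needs one, so 28/2 = 14 days.
- 60+90 mg: no combination gives 30 mg, so 0 days over any period.

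**2. Tolvaptan titration and run-in**

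Supplied: 2 x 4 x 7 = 56 tablets of 15 mg and 56 of 45 mg. Under Section 6.1, the daily use of 15 mg tablets is 1, 3 and 2 at the three steps. With weekly steps from Day -28 and a one-week run-in:
- Full up-titration: 7 + 21 + 14 + 14 = 56 of 56. Covered, with no spare tablet.
- 45/15 mg throughout: 4 x 7 = 28 of 56. Covered.
- Held at 60/30 mg from week 2 through run-in: 7 + 21 x 3 = 70 against 56, so 14 short.

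Run-out on the held path: by the end of Day -6, 7 + 16 x 3 = 55 tablets are used and one is left. On Day -5 that tablet can complete the morning dose but not the afternoon one. Spare 45 mg tablets (28 of 56 used on this path) cannot make 30 mg. Days -5 to -2 cannot be fully dosed, nor can any Day -1 dose due before that visit.

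**3. Metformin titration and run-in**

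Supplied: 2 x 30 = 60.
- Full up-titration: 7 + 14 + 21 + 21 = 63, so 3 short. Use by the end of Day -2 is 7 + 14 + 13 x 3 = 60, so all three missing tablets belong to Day -1.
- Held at 500/500 mg: 7 + 14 + 14 + 14 = 49. Covered.

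**4. Sensitivity to the dates**

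Randomization is on Day -29 in Section 4 and on Day -30 in Section 4.2. Section 4.1 starts drug the next day, so the start is Day -28 or Day -29. Day -22 and Day -15 in Section 4.3 can be read as days of the tolerability check (new dose from Days -21 and -14) or as days of the dose change.

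| Start; dose changes | Metformin, full (60 supplied) | 15 mg, full (56 supplied) | 15 mg, held at 60/30 mg (56 supplied) |
|---|---|---|---|
| -28; -21 and -14 | 63 | 56 | 70 |
| -29; -21 and -14 | 64 | 57 | 71 |
| -28; -22 and -15 | 65 | 57 | 72 |
| -29; -22 and -15 | 66 | 58 | 73 |

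On the last three rows, the missing tolvaptan tablets with full up-titration (1 or 2) still fall on Day -1. For metformin, 1, 2 and 3 tablets respectively are also missing on Day -2.

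**The case against.** The strongest reply on the packages is that the sentence fixes how many packages are given, not which type, and that no period is stated. The two 14-day figures then assume that a 90/30 mg patient receives a 15+45 or 30+60 mg package, which no section says. This narrows the point but does not remove it. The package left over for the third step is 60+90 mg, and it cannot make 90/30 mg over any period. Combining packages would supply the dose, but that is no longer one package.

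Three stronger readings are tempting, and the documents do not support them.

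- A reader might infer that the titration and run-in counts fall short in general. On the weekly steps, tolvaptan with full up-titration is exactly covered. The metformin gap falls on a day with scheduled dispensing, so at most a dose due before that visit is affected.
- A reader might set the on-treatment counts against visits that are 84 days apart (metformin throughout, tolvaptan after Month 18; Section 4.5) and infer a large shortage. The counts carry no stated period and fit about a month: 60/2 = 30 and 90/3 = 30 days for metformin, and 28 days for tolvaptan at the lower two steps. If they are monthly there is no shortfall. Figures 2 and 4 are not reproduced in the text reviewed, so a schedule there cannot be excluded. I make no finding on this.
- A reader might infer that the third package implies a 90/60 mg regimen. No section states such a step. The text shows a conflict, not which side is right.

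**Conclusion.** The point stands in two parts.

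First, the 60+90 mg package conflicts with the stated top step, and the one-package sentence fails for patients kept at 90/30 mg: 14, 14 or 0 of 28 days by package type. The day counts at the lower steps and the 28-day yardstick rest on an inferred period. The mismatch of the third package does not.

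Second, one permitted tolvaptan path, held at 60/30 mg through run-in, is 14 tablets of 15 mg short on weekly steps from Day -28. Supply is insufficient from Day -5, with no scheduled dispensing until Day -1. Other readings of the dates raise the shortfall to between 15 and 17 tablets. The metformin gap of 3 tablets is minor on weekly steps from Day -28.

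These are errors in the operating text that should be corrected. They do not touch the endpoint, analysis or sample size, and they rank below points that do.

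**What to change.** 1. Reconcile the package contents in Section 6.2.2 and the one-package sentence in Section 6.1 with the dose steps in Sections 2.2.4, 4.3 and 6.1. This review takes no view on which is right.
2. Reconcile the randomization day (Sections 4 and 4.2), and state whether Day -22 and Day -15 in Section 4.3 are check days or dose-change days.
3. From the reconciled steps and dates, recompute the first-visit supply so that every permitted path is covered to the Day -1 dispensing visit, including doses due that day before it.

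The cost is protocol and pharmacy wording, a recount and possibly a few more tablets. If the steps in Section 6.1 and a Day -28 start are kept, the held 60/30 mg path needs 7 + 20 x 3 = 67 tablets of 15 mg to the end of Day -2. The Day -1 waking dose makes it 68, which is 12 more than supplied; covering all of Day -1 takes 14 more. Metformin would need one more tablet for the Day -1 waking dose, or three for the whole day. No visit, contact or patient is added, and the design does not change.
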